#### Power analysis and sample size justification

We conducted a power analysis based on the primary endpoints of change in CVR and CBF and correlation of CBF/CVR and symptoms/cognition. Based on the preliminary results, we assume the average changes in CVR between treatment and placebo has an effect size of 0.86. With 50 concussed boxers in each arm, assuming that the correlation between the outcome measures at Day 1-3 and 30 is 0.2, we will achieve 80% power to detect difference in CVR changes comparing sildenafil and placebo effects. If the correlation is 0.5 among outcome measures at all time-points, then with 80% power we only need 34 concussed boxers in each arm. Table 1 demonstrates the needed sample size under a range of effect sizes and within-subject correlations. To understand the correlation between the CVR and post-concussive symptoms among the 50 enrolled boxers (for each group) assessed at three time points, we will have 82.9% power to detect a correlation of 0.4 based on the preliminary results in Table 1 with 95% confidence level.

	Correlation between 3, time-points (rho)							
	0	0.2	0.3	0.5	0.6	0.7	0.8	
Corresponding SD	1.414	1.265	1.183	1	0.894	0.775	0.632	
Effect size	Sample size needed							
0.7	46	38	33	25	21	16	12	
0.86	32	26	23	18	15	12	9	
1	24	20	18	14	12	10	8	
1.2	18	15	14	11	9	8	6	

Table 1: Sample size for each treatment and placebo group under a range of effect sizes and within-subject correlations to achieve 80% power.

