Also, we will assess the treatment effect of sildenafil on post-concussive symptoms and cognitive performance using two-sample t-test similarly as in the primary aim, but with the secondary endpoints of symptoms. On day 1 and 30 after injury we will then calculate the difference in CBF/CVR and each of the post-concussive symptom assessments and cognitive assessments after the single treatment of sildenafil. Also, we will assess the post-concussion correlations of CBF/CVR and cognitive performance by calculating the cross-sectional Pearson correlations of CBF/CVR with symptom inventory and neuropsychological CDEs collected at Day 1 and 30 after TBI. Correlations will be calculated separately and jointly at each time point, and for each of the subdomains of neuropsychological CDEs. Multiple comparisons will be adjusted by controlling the false discovery rate (FDR).

Our secondary analyses will consist of assessing the treatment effect of sildenafil therapy on brain biomarker levels using two-sample t testing, but with the secondary endpoints of symptoms. We will then calculate the difference in brain biomarker levels at the beginning of the sildenafil therapy and after the treatment period (Day 30 vs Day 1-3). Scatter plots including both arms will be generated based on the calculated differences and two linear regression models with changes in brain biomarkers as outcomes, and changes in symptoms as independent variables will be fit to assess the association between the recovery of the TBI-related markers. Potential confounders such as gender and treatment arm indicator will be adjusted in the model.

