#### Alternative strategies:

For our primary analysis, if CBF or CVR is not normally distributed based as shown in Q-Q plot, a nonparametric Wilcoxon rank-sum test will be used instead. And for our secondary analysis, if we are not powered to identify correlations of biomarkers with subdomains of symptoms and neuropsychological CDEs after multiple comparison correction, we will use dimension reduction approaches such as principal component regression (PCR) on CDEs to group panels of symptom assessments. The resulting panels of symptoms are selected to explain most of the variations across subjects and will be most correlated with brain biomarkers.

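### The CVR sample sizes in the text (50 and 34 per arm) contradict Table 1 (26 and 18), Table 1 fits a paired test and not the planned two-sample test, and neither alpha nor the powered comparison is stated

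*Combined protocol and SAP*

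**What the plan says.** The power section of SAP section 10.1 takes an effect size of 0.86 for the difference in CVR change between sildenafil and placebo.

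- **Correlation 0.2.** "With 50 concussed boxers in each arm, assuming that the correlation between the outcome measures at Day 1-3 and 30 is 0.2", the plan says "we will achieve 80% power to detect difference in CVR changes comparing sildenafil and placebo effects".
- **Correlation 0.5.** "If the correlation is 0.5 among outcome measures at all time-points, then with 80% power we only need 34 concussed boxers in each arm".
- **The section's own Table 1** is captioned "Sample size for each treatment and placebo group under a range of effect sizes and within-subject correlations to achieve 80% power". Its row for effect size 0.86 reads 32, 26, 23, 18, 15, 12, 9 for correlations 0, 0.2, 0.3, 0.5, 0.6, 0.7, 0.8. Above it stands a row of SDs: 1.414, 1.265, 1.183, 1, 0.894, 0.775, 0.632.
- **Alpha.** None is given for CVR. The only confidence level belongs to a separate claim, 82.9% power to "detect a correlation of 0.4 based on the preliminary results in Table 1 with 95% confidence level". That claim counts boxers differently: "among the 50 enrolled boxers (for each group) assessed at three time points".
- **Test.** Under Statistical analyses, symptoms and cognition are compared "using two-sample t-test similarly as in the primary aim". Under Alternative strategies, if CBF or CVR is not normal, "a nonparametric Wilcoxon rank-sum test will be used instead".
- **Design.** Section 4.1 describes two regimen groups (single dose; 14 daily doses) of about 50 athletes each. Section 10.2.1 randomises 1:1 to sildenafil or placebo. Section 4.2.1 hypothesises a benefit for both regimens.
- **Enrolment.** Section 4.1 caps it at 100; section 10.2.1 plans 110 to 120, with 10-20% dropout.

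**The concern.** The same section gives two required sample sizes for the same inputs: 34 and 18 per arm at correlation 0.5. The planned 50 at correlation 0.2 stands beside a table value of 26. The table's SD row is that of a within-person difference, and its numbers are too small for a comparison of two independent arms at 5%.

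This section is the only sample-size justification for CVR, a primary endpoint. If the regimens are judged separately, each comparison has about 25 per arm, and a reader would set a null result against a printed 80% that does not apply to it. The plan also says, under Stopping rules, that the trial's data will feed a power analysis for a definitive study, so a paired calculation could carry forward.

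**Working it through.** **Inputs.** Effect size 0.86, the SD row, the Table 1 cells, and the text figures 50 and 34, all from the power section. Two-sided 5% for CVR is an assumption, because the plan gives none. I read 0.86 as the table uses it, as a difference to be divided by the SD in the table.

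**Step 1: the SD row.** SD = √(2(1−ρ)). At ρ = 0.2, √1.6 = 1.265; at ρ = 0.5, √1 = 1. All seven entries match. This is the SD of the difference between two measurements with unit SD and correlation ρ. The standardised effect is d = 0.86/1.265 = 0.680 at ρ = 0.2, and d = 0.86 at ρ = 0.5.

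**Step 2: reproducing Table 1.** Exact noncentral-t power, smallest n with at least 80%:

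- paired (one-sample) t: df = n − 1, noncentrality d√n
- two-sample t, n per arm: df = 2n − 2, noncentrality d√(n/2)

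| Test and alpha | Cells matched (of 28) | n at ρ 0.2 | n at ρ 0.5 |
|---|---|---|---|
| Table 1 as printed | – | 26 | 18 |
| Paired, two-sided 0.05/3 | 28 | 26 | 18 |
| Paired, two-sided 5% | 0 | 19 | 13 |
| Two-sample, two-sided 5% | 3 | 35 | 23 |
| Two-sample, one-sided 5% | 7 | 28 | 18 |
| Two-sample, two-sided 0.05/3 | 0 | 47 | 30 |

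The 0.05/3 is inferred from the fit; the plan does not state it.

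**Step 3: the text figures.** Two-sided 5% in a two-sample test requires 35 and 23, not 50 and 34. A stricter alpha comes closer: 0.0125 gives 50 and 32. But 50 is exact at alpha 0.0123 and 34 at 0.0090, so no single alpha makes both exact requirements.

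**Step 4: power of the printed numbers in the planned two-sample t-test, two-sided 5%.**

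| Reading | ρ 0.2 | ρ 0.5 |
|---|---|---|
| Text, per arm (50; 34) | 92% | 94% |
| Text as regimen totals (25 v 25; 17 v 17) | 65% | 68% |
| Table 1, per arm (26; 18) | 67% | 71% |

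The planned 25 v 25 within a regimen has 65% at ρ = 0.2 and 85% at ρ = 0.5. It first reaches 80% at ρ of about 0.44.

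**Step 5: attrition at ρ = 0.2, two-sided 5%.**

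- 100 enrolled less 10-20% leaves 80-90, so 40-45 per pooled arm: 85-89% power. Within a regimen (20 v 20 to 22 v 23): 55-61%.
- 110-120 enrolled leaves 88 (110 × 0.8) to 108 (120 × 0.9), so 44-54 per pooled arm: 88-94%. Within a regimen (22-27 per arm): 60-69%.

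**Step 6: the correlation claim.** With Fisher's z, n = 50, r = 0.4 and two-sided 5%: artanh(0.4) × √47 − 1.96 = 0.4236 × 6.856 − 1.96 = 0.944, and Φ(0.944) = 82.8%, against 82.9% printed. That claim reproduces, and in it 50 is a group total.

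**The case against.** The strongest reply has five parts.

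- **50 may be planned enrolment, not a requirement.** With 100 athletes at 1:1, 50 per arm would simply reach at least 80%. This softens 50 v 26. It does not touch 34, which is expressly the number needed, against 18 in the table.
- **The mismatch with 80% depends on the assumed 5%.** At 0.05/3, 50 per arm at ρ = 0.2 gives 83%; at 0.0125 it gives 80.2%, and 34 at ρ = 0.5 gives 83%. So the text may be approximate two-sample figures at a stricter, unstated alpha, and the false-discovery-rate control and several primary endpoints leave room for one. This stands as a reason to obtain the alpha before replacing any figure. It confirms that the plan cannot be checked as written.
- **A rounding and labelling slip could explain the gap.** The table's method gives unrounded n of 25.58 and 17.11. Rounded up, these are 26 and 18; truncated and doubled, 50 and 34. This is plausible, but the text would then be wrong to say per arm, power at 25 and 17 would be 78.8% and 79.6% by the table's own method, and the method would still be paired.
- **The plan mentions sildenafil and placebo periods** (Primary analyses), which suits a within-person comparison. Sections 4.1 and 10.2.1 nevertheless describe parallel arms.
- **This is a pilot, and pooled it is adequately sized.** The second half is right: 92% at 5%, and 83% at 0.05/3. The 65% applies only to a per-regimen comparison at ρ = 0.2 and 5%. But the plan makes a formal power claim, and its size is not what is criticised here.

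**Conclusion.** The concern holds, and the section needs correcting. The conflict between 34 and 18 per arm is on the page and needs no assumption. Table 1 does not describe the planned two-sample test: its 26 and 18 per arm give 67% and 71% power at two-sided 5%, not 80%. That a paired test at 0.05/3 generated the table is an inference from an exact 28-cell match.

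The CVR alpha, its sidedness and the powered comparison are all unstated. At ρ = 0.2 and an assumed two-sided 5%, the printed 80% for 50 boxers fits neither reading: 92% pooled, 65% within a regimen. None of this shows that the pooled comparison is too small. It shows that the claimed power cannot be verified, and that a regimen-specific comparison may have well under 80%. The power figures rest on 0.86 being scaled by √(2(1−ρ)) and, except in Step 5, on no attrition.

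**What to change.** 1. **State alpha and sidedness for CVR**, allowing for whatever multiplicity control is intended. The figures below are for two-sided 5% and should be final only once that alpha is confirmed.
2. **Replace Table 1 with two-sample values.** At two-sided 5%:

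| Effect size | ρ 0 | 0.2 | 0.3 | 0.5 | 0.6 | 0.7 | 0.8 |
|---|---|---|---|---|---|---|---|
| 0.7 | 66 | 53 | 46 | 34 | 27 | 21 | 14 |
| 0.86 | 44 | 35 | 31 | 23 | 18 | 14 | 10 |
| 1 | 33 | 27 | 23 | 17 | 14 | 11 | 8 |
| 1.2 | 23 | 19 | 17 | 12 | 10 | 8 | 6 |

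3. **Say what 50 counts.**
   - Pooled regimens: keep 50 per arm, restate power as 92% at ρ = 0.2, replace the required 34 by 23, and report regimen-specific effects as estimates with confidence intervals.
   - Per regimen: relabel 50 as the regimen total, print the 25 v 25 power (65% at ρ = 0.2, 85% at ρ = 0.5), and give required totals of 70 (2 × 35) and 46 (2 × 23).
4. **If the sponsor confirms that 0.05/3 was intended**, use that alpha throughout: 47 and 30 required per arm, with 83% pooled and 48% per-regimen power at ρ = 0.2.
5. **Reconcile enrolment** of 100 with 110-120, and base the stated power on expected completers.

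The cost is wording and figures in the SAP and protocol. The correction itself adds no participants, but if the comparison is per regimen, the plan would have to show 65% and not 80% at ρ = 0.2.

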#### 4.2.1.b. TBI Neuropsychological Assessments

In this clinical study, we test whether sildenafil improves cognitive, mood, and functional outcomes in injured boxers. The testing procedures will be conducted in a quiet room at UTSWMC by a neuropsychologist or trained coordinator. We anticipate that the testing procedures will take approximately 1 hour to complete. The subjects will be given frequent rests and they have the right to refuse to answer any questions or to stop a test at any time and for any reason. TBI phenotyping instruments recommended for evaluation in all TBI cohort or natural history studies have been labeled the TBI Common Data Elements (CDEs)(58). The subject will be interviewed, complete questionnaires, take pen-and-paper tests, and perform simple actions.

In this study we will include the following selected subset of assessments taken from the CDE's:

- Hopkins Verbal Learning Task (HVLT). The **Hopkins Verbal Learning Test** (HVLT) is a brief verbal learning and memory test with six alternate forms of 12 words.
- The Sport Concussion Assessment Tool (SCAT5), from the Concussion in Sport Group, is a standardized tool for evaluating injured athletes for concussion and can be used in athletes aged 13 years and older. This test will take approximately 30 minutes.
- Satisfaction with Life Scale (SWLS): is a short 5-item instrument designed to measure global cognitive judgments of satisfaction with one's life. The scale usually requires only about one minute of a respondent's time.
- Rivermead Post-Concussion Symptom Questionnaire: rate the severity of 16 different symptoms commonly found after a TBI (5 min).
- Galveston Orientation and Amnesia Test (GOAT)-modified for sports athletes

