## 10.2 MEASURES TO MINIMIZE BIAS

## 10.2.1 ENROLLMENT/ RANDOMIZATION/ MASKING PROCEDURES

#### Recruitment Methods and Consenting Process:

At the baseline visit, the participants will be consented to participate in the study. After participating in the boxing match, the enrolled boxers will be re-screened and if the boxer has a Rivermead symptom score > 1 on at least 3 items from the Rivermead Post-Concussion Questionnaire or has greater than 25 blows to the head, the participant will be informed of their eligibility to participate in the study and the potential risks associated with this clinical trial.

A copy of the signed consent form will be provided to the participant/family, and one copy will remain in a locked storage facility. Both women and minorities will be enrolled in this study. Due to the study population, children will not be enrolled in this study. Previously, we have enrolled 125 boxers from the North Texas area to participate in both observational and interventional clinical trials. Recently we completed a Department of Defense (DOD) observational study aimed at measuring early brain biomarkers of injury in professional boxers. We identified numerous early predictors of outcome in these athletes. Our dropout rate is very low and previously the boxers were compliant with the study procedures (self-administering study medication, neuropsychological testing, MRI procedures). We expect a dropout rate of 10-20% and will enroll a total of 110-120 boxers to complete the proposed studies.

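### The stated 82.9% power for a correlation of 0.4 belongs to one unadjusted test, whereas the plan tests a family of correlations under FDR control and so has lower power

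*Combined protocol and SAP*

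**What the plan says.** The power section of 10.1 names the correlation of CBF/CVR with symptoms and cognition among the primary endpoints on which the power analysis was based. For CVR and post-concussive symptoms, "among the 50 enrolled boxers (for each group) assessed at three time points", it states that "we will have 82.9% power to detect a correlation of 0.4", "based on the preliminary results in Table 1 with 95% confidence level". It mentions no allowance for multiple testing or dropout.

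The Statistical analyses part of 10.1 describes the analysis itself. Associations are assessed "by calculating the cross-sectional Pearson correlations of CBF/CVR with symptom inventory and neuropsychological CDEs collected at Day 1 and 30 after TBI". It continues: "Correlations will be calculated separately and jointly at each time point, and for each of the subdomains of neuropsychological CDEs". The next sentence reads: "Multiple comparisons will be adjusted by controlling the false discovery rate (FDR". Neither the FDR level nor the number of correlations is given.

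On losses, 10.2.1 (Recruitment Methods and Consenting Process) says "We expect a dropout rate of 10-20" per cent, and the same sentence plans to enrol 110-120 boxers to allow for it. Section 4.1 and 10.2.1 (Drug Treatment and Randomization) give 100 as the number enrolled, and the power statement calls its 50 per group enrolled.

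**The concern.** The power figure and the analysis describe different tests. A single correlation is tested at 0.05. A correlation inside a family under FDR control is tested at a threshold that can fall as low as the FDR level divided by the number of tests. At a 5% FDR level the Benjamini-Hochberg threshold never exceeds 0.05, so power per correlation cannot exceed the single-test figure and is usually well below it.

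The 82.9% forms part of the sample size justification. A reader would take it as the chance that the planned analysis finds a true correlation of 0.4. If it is not, a null result could be read as evidence against an association that the study was unlikely to detect.

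**Working it through.** **Inputs from the documents.** r = 0.4, 50 per group and 95% confidence (power section); FDR control and two post-injury visits (Statistical analyses); five instruments (4.2.1.b: HVLT, SCAT5, SWLS, Rivermead, GOAT). Table 1 in the power section gives sample sizes for mean changes and no CVR-symptom correlation, so 0.4 is taken as given.

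**Assumptions.** Two-sided tests; 5% FDR by Benjamini-Hochberg; independent tests; a family of 2 vascular measures × 5 instruments × 2 visits = 20, before subdomains or brain regions.

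**1. Reproducing 82.9%.** Fisher z power = Φ(atanh(r)·√(n − 3) − z), with atanh(0.4) = 0.4236.
- n = 50: 0.4236 × √47 = 2.904; Φ(2.904 − 1.960) = 82.8%. Direct simulation of the Pearson test gives 83.5%.
- Variants that do not match: one-sided, about 90%; n = 25, 51%; n = 100, 98.7%; n = 150, 99.9%.

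The stated figure is therefore one unadjusted test with one observation per participant and no losses.

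**2. Under FDR, n = 50, 20 tests.** The strictest step is 0.05/20 = 0.0025, critical value 3.023: Φ(2.904 − 3.023) = 45.3%. Power of the full procedure, by simulating independent Fisher z statistics:

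| Real correlations of 0.4 among 20 | Power per real correlation |
|---|---|
| 1 | 46% |
| 5 | 61% |
| 10 | 71% |
| 20 | 80% |

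Simulating Pearson coefficients directly gives 46%, 62%, 72% and 81%.

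**3. Enrolment.** Completers per group = enrolled × (1 − dropout)/2.

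| Enrolled | Dropout | Per group | Unadjusted power |
|---|---|---|---|
| 110 | 10% | 49.5 | 82% |
| 120 | 20% | 48 | 81% |
| 110 | 20% | 44 | 77% |
| 100 | 10% | 45 | 78% |
| 100 | 20% | 40 | 73% |

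At the strictest step of the 20-test family:
- n = 45: Φ(0.4236 × √42 − 3.023) = Φ(−0.278) = 39%.
- n = 40: Φ(0.4236 × √37 − 3.023) = Φ(−0.446) = 33%.

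**4. Only if visits were stacked.** Suppose two visits per person enter a plain Pearson test and both variables have within-person correlation ρ. The null variance of the coefficient is then inflated by 1 + ρ². Type I error is 2·[1 − Φ(1.96/√(1 + ρ²))]:
- ρ = 0.2: factor 1.04, 5.5%.
- ρ = 0.5: factor 1.25, 8.0%.
- ρ = 0.8: factor 1.64, 12.6%.

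**The case against.** The arithmetic behind 82.9% is right, and the sentence concerns one named relation, CVR with symptoms, not the whole set of cognitive measures. The family size, the FDR level and independence are assumptions. Quoting about 45% alone would present the worst case as the answer: FDR is less severe than Bonferroni when many correlations are real, and the protocol's premise is that CVR relates to both symptoms and cognition. The data are also meant to inform a later definitive study. All of this limits the size of the loss. It does not remove the mismatch, because the CVR-symptom correlation belongs to the set placed under FDR control. The Alternative strategies text foresees low power after correction only for the biomarker correlations, so its fallback does not cover this analysis.

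Two stronger readings are tempting. One is that dropout alone brings completers down to 40-45 per group. The sentence on dropout also provides for enrolling 110-120. When enrolment and loss are matched (110 at 10%, 120 at 20%), about 48-50 per group remain and unadjusted power is 81-83%. The lower numbers follow only if enrolment stops at 100.

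The other is that the plan pools repeated visits as if they were independent. No text says so. The correlations are called cross-sectional, and *jointly* is tied to each time point without definition. The stated power does not come from 100 or 150 stacked observations, and stacking would raise power, not lower it. What remains is an undefined term. The power section also speaks of three time points where the analysis uses two.

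**Conclusion.** The point holds in this form: 82.9% is the power of one unadjusted test with 50 complete participants, and the analysis described has less. With 20 independent tests at 5% FDR and n = 50, power per true correlation of 0.4 runs from about 46% (one real) to 80% (all real). It comes close to the stated figure only if nearly every correlation is real. A larger family would lower the bottom of the range; a laxer FDR level would raise the figures.

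The dropout issue is an inconsistency in planned enrolment, not a missing allowance. If 100 is the cap, power is 73-78% unadjusted and about 33-39% at the strictest step of the assumed family. The type I error of 5.5% to 12.6% is conditional on a stacked analysis that the documents do not specify. The documents give no within-person correlation for symptoms, so the values of ρ used for both variables are illustrative; the range 0.2 to 0.8 lies within that of Table 1.

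**What to change.** - State the FDR level and procedure, and list the correlations in the family (measures, instruments or subdomains, visits, groups).
- Label 82.9% as the unadjusted power of a single test in 50 complete participants. Give the FDR-adjusted range as the power of the planned analysis, recomputed for the listed family and for several numbers of true correlations.
- Reconcile the enrolment figures in 4.1, in both parts of 10.2.1 and in the power section, and base the power on expected completers.
- Define *jointly*. If visits are combined, use a mixed model or another method with a participant effect, not a plain Pearson test on stacked values. Align the number of time points in the power and analysis text.

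The cost is SAP wording and a less favourable stated power. These changes add no participants beyond those the protocol already mentions.
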